4.1. Primary Endpoint

Table 1: Primary Objective Estimand

Objective	To evaluate the allergen-induced LAR 3 to 7 hours after the administration of the allergen inhalation challenge between subjects treated with zavegepant and placebo.
Efficacy Endpoint	Maximum percentage decrease from baseline in FEV ₁ at any time between 3 and 7 hours post-allergen challenge in the modified intent-to-treat (mITT) analysis set.
Summary	Difference in maximum percentage decrease from baseline in FEV ₁ between the zavegepant and placebo groups using an ANCOVA model.
Intercurrent Events	Treatment policy strategy : All available assessments on the subject are used regardless of intercurrent events.

4.2. Secondary Endpoints

Table 2: Secondary Objective Estimands

1 Objective	To evaluate the allergen-induced EAR 0 to 2 hours after the administration of the allergen inhalation challenge between subjects treated with zavegepant and placebo.
Efficacy Endpoint	Maximum percentage decrease from baseline in FEV ₁ at any time between 0 and 2 hours post-allergen challenge in the mITT analysis set.

This document is confidential.

	Summary	Same as that of primary estimand, with respect to EAR.
	Intercurrent Events	Treatment policy strategy : All available assessments on the subject are used regardless of intercurrent events.
2	Objective	To evaluate the AHR measured at 24 hours post-allergen challenge between subjects treated with zavegeptan and placebo.
	Efficacy Endpoint	Shift from pre-allergen challenge (Visit 6) to post-allergen challenge (Visit 8) of PC ₂₀ in the mITT analysis set.
	Summary	Difference in shift from pre to post-allergen challenge between the zavegeptan and placebo groups using an ANCOVA model.
	Intercurrent Events	Treatment policy strategy : All available assessments on the subject are used regardless of intercurrent events.
3	Objective	To assess the safety and tolerability of oral zavegeptan.
	Endpoint	Various safety endpoints (i.e., adverse events, clinically significant laboratory abnormalities).
	Summary	Frequency by treatment group of safety endpoints for the safety analysis set.
	Intercurrent	Not applicable

This document is confidential.

5. Analysis Sets, Treatment Groups, and Subgroups

5.1. Analysis Sets

Enrolled: The enrolled analysis set includes all subjects who sign the informed consent form (ICF) and are assigned a subject identification number by the IWRS.

Full: The full analysis set includes enrolled subjects who receive a randomization treatment assignment from the IWRS.

Safety: The safety analysis set includes subjects from the full analysis set who received at least 1 dose of study therapy. The safety analysis set will be used for all analyses of safety endpoints. Subjects will be analyzed according to the treatment actually received.

Modified Intent-to-Treat (mITT): The mITT analysis set includes safety subjects (received at least 1 dose of study therapy) that provided at least 1 non-missing post-baseline LAR assessment. Subjects will be analyzed according to randomized treatment assignment.

Follow-up: Safety subjects whose last contact date is in the follow-up analysis period. This analysis set is used to assess follow-up safety.

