15.2 Analysis Populations

Enrolled population: The enrolled population will include all subjects who sign the ICF and are assigned a subject identification number.

Randomized population: Enrolled subjects who receive a randomization treatment assignment from the IWRS.

Treated population: Randomized subjects who received at least 1 dose of study therapy.

Modified Intent-to-Treat (mITT) population: Randomized subjects that received at least 1 dose of study therapy and provided at least 1 non-missing post-baseline LAR assessment.

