5.2. Treatment Groups

The two treatment groups are zavegepant and placebo. The safety analysis set is assessed by as-treated treatment group, the full and mITT analysis sets are assessed by as-randomized treatment group, and the enrolled analysis set is assessed overall.

If a subject receives ≥ 1 dose of planned randomized treatment then that subject is considered to have as-treated treatment group equal to as-randomized treatment group, and will be analyzed according to randomized treatment.

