- Did not complete the study (identified as those with “no” response to the question “Did the subject complete the study?”)
 - Reasons for not completing the study, including not reported
- Terminated the study prematurely due to COVID-19. This has the same subcategories as “Did not complete the study.”

7.4. **Protocol Deviations**

A relevant protocol deviation is a deviation from the protocol which is programmed from the database and which could potentially affect the interpretability of the study results. This type of deviation includes but is not limited to:

- Eligibility
- Subject management

The frequency table of relevant protocol deviations displays the number and percentage of subjects in deviation categories and subcategories by deviation type (e.g., eligibility, subject management) for the full analysis set. Results are displayed for all deviations, even those with 0 counts, unless otherwise specified. See Section 6.2.4.1 of the Core SAP for further details.

A by-subject listing of relevant, programmable protocol deviations is provided for the enrolled analysis set. Relevant protocol deviations are outlined in [Section 16](#).

A by-subject listing of significant protocol deviations is provided for the enrolled analysis set. This includes visit, type, and description, which are used as additional sorting variables.

A Microsoft Excel file of protocol deviations is provided by the data management vendor from the clinical trial management system (CTMS). This file serves as the raw data source of protocol deviations, and classifies deviation severity as major, minor, or exclude. Significant protocol deviations are defined as those with major severity. A footnote describes the raw data source and how significant protocol deviations are identified, e.g., “Significant protocol deviations are those with major severity reported by the data management vendor in the clinical trial management system.”

7.5. **Demographic and Baseline Characteristics**

A summary of demographic and baseline characteristics will be presented by treatment group and overall using the safety analysis set. Descriptive statistics will be calculated for continuous variables (age, BMI, height, and weight) at baseline. Frequency counts and percentages will be tabulated for categorical variables (age category, gender, childbearing potential if female, ethnicity, race, country, BMI category).

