7.9. Extent of Exposure

Study drug is zavegeptan 300 mg daily, i.e., six 25 mg softgel capsules twice daily, taken in the morning and the evening. Study drug is dispensed in a wallet-type blister pack with a unique wallet ID and 8 wallets are placed into a subject specific kit with a unique kit ID. Each wallet covers 4 days of morning dosing (6 capsules) and evening dosing (6 capsules) dosing, for a total of 48 capsules. Sites will record the kit and wallet IDs dispensed to each subject on the Drug Accountability CRF.

Subjects report study drug exposure in the eDiary, whereas sites report study drug accountability in the Drug Accountability CRF.

This document is confidential.

Study drug exposure is tabulated as continuous or categorical variables by treatment group and overall for the safety analysis set and includes the following parameters:

- Time from study drug start to last contact (days), derived as: last contact date – study drug start date + 1
- Time on study drug (days), derived as: study drug end date – study drug start date + 1
- Time on study drug categories (weeks): 1, 2, 3, 4, or > 4
- Cumulative study drug exposure (mg), derived by summing {number of capsules × 25} across records with complete study medication start dates
- Average study drug exposure (mg per day), derived as cumulative study drug exposure/time on study drug (days)
- Total study drug exposure (mg) summed across all subjects, derived by summing cumulative exposure across all subjects
- Total study drug exposure (patient-years), derived by summing (study drug end date – study drug start date + 1)/365.25 across all subjects.

Study drug accountability is tabulated by treatment group and overall for the safety analysis set that includes the number and percentage of subjects in the following category:

- Study drug taken but subject not randomized
- Kit dispensed and all 8 wallets returned
- Kit dispensed and all 8 wallets not returned
 - Reason for wallets not being returned
- Number of capsules returned
- Number and percentage of subjects who took > 12 capsules on any 1 day
- Any partial/missed doses
- Compliance < 80%, derived as: (number of capsules dispensed – number of capsules returned)/(number of capsules expected to be taken) × 100%
- No study drug taken for ≥ 3 days (not necessarily consecutive) in any 1 week
- Incorrect study drug taken: all the time, or at least once

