Appendix A Relevant Protocol Deviations

Relevant eligibility protocol deviations include the following categories:

- Respiratory disease other than mild intermittent asthma
- Baseline FEV₁ < 70% of predicted value
- Score on the Sheehan-Suicidality Tracking Scale (S-STS) at screening > 0
- Methacholine challenge (PC₂₀ > 16 mg/mL)
- History of liver disease or viral hepatitis
- History of HIV
- Use of tobacco products and/or vaping products within the previous 12 months or smoking history > 10 pack years.
- Positive drug screen
- Findings out of range, defined any as any of the following subcategories:
 - At any time during the study:
 - Females with a positive pregnancy test
 - During pre-treatment period:
 - ALT \geq 1.5x ULN
 - AST \geq 1.5x ULN
 - Direct bilirubin \geq 1.5x ULN
 - Indirect bilirubin \geq 1.5x ULN
 - Total bilirubin \geq 1.5x ULN
 - BMI \geq 33 kg/m²
 - Estimated glomerular filtration rate (eGFR) according to the re-expressed abbreviated (4-variable) Modification of Diet in Renal Disease (MDRD) Study equation \leq 40 mL/min/1.73m²
 - Systolic blood pressure > 150 mmHg
 - Diastolic blood pressure > 100 mmHg

Relevant subject management protocol deviations include the following categories:

- Study drug dosing
 - < 80% compliance
- Study drug dosing error, defined as any of the following subcategories:
 - Study drug taken but not randomized
 - Study drug actually received different from randomized treatment assignment
- Missed study exit visit
- Missed methacholine challenge, skin allergen challenge, allergen challenge
- Washout period after methacholine challenge and sputum induction on Visit 4 other than 2-4 weeks
- Visit 5 methacholine challenge FEV₁ < 90% of baseline for FEV₁
- Visit 9 (follow up onsite visit) conducted outside 7-10 day after last study treatment window
- Use of any prohibited medications (refer to Table 9.1 in the protocol) on or after informed consent
 - CGRP targeting medications
 - Anti-IgE therapy
 - Allergy immunotherapy
 - Investigational drug
 - Systemic, inhaled, topical nasal steroids
 - Immunosuppressives
 - Anticoagulants
 - Theophylline
 - Nedocromil or cromoglycate
 - Modafinil

This document is confidential.

- St. John's wort
- Atypical antipsychotics such as aripiprazole, olanzapine, quetiapine, risperidone, ziprasidone
- Mood stabilizers such as lithium, lamotrigine or divalproex/valproic acid/valproate

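### Both planned counts of dosing without randomisation are zero by construction and the safety summaries omit such a subject; the as-treated wording also needs reconciling for mixed exposure

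*SAP*

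**What the plan says.** SAP 5.1 builds its sets in sequence. First: "The full analysis set includes enrolled subjects who receive a randomization treatment assignment from the IWRS". Then: "The safety analysis set includes subjects from the full analysis set who received at least 1 dose of study therapy". The protocol's counterpart, the Treated population in section 15.2, carries the same restriction: "Randomized subjects who received at least 1 dose of study therapy".

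Two planned outputs look for subjects outside those sets:

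- SAP 7.9: "Study drug accountability is tabulated by treatment group and overall for the safety analysis set". Its first category is "Study drug taken but subject not randomized".
- SAP 7.4 gives the frequency table of relevant deviations "by deviation type (e.g., eligibility, subject management) for the full analysis set". Appendix A lists, among the dosing errors to be counted there, "Study drug taken but not randomized".

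On treatment grouping, SAP 5.1 says that safety subjects are analysed by the treatment they actually got. SAP 5.2 then adds: "If a subject receives ≥ 1 dose of planned randomized treatment then that subject is considered to have as-treated treatment group" equal to the randomised group. SAP 7.9 foresees wrong-kit dosing and separates subjects with the wrong drug at least once from those with the wrong drug throughout.

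**The concern.** The plan expects that someone might be dosed without being randomised and asks for a count, but takes the count in sets that exclude the person by definition. A reader of the report would see a zero in two tables and take it as evidence that the error did not happen. If it did happen, the subject's adverse events, laboratory values and vital signs would be missing from the summaries that answer the safety objective, because SAP section 10 runs all safety analyses on the safety set.

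The second issue is about labels. The general sentence in SAP 5.1 points to the drug received. The rule in SAP 5.2 keeps the randomised label after a single correct dose. For a placebo subject who then takes zavegepant from a wrong kit or wallet, the two give different columns. Under SAP 5.2, that subject's zavegepant exposure and events are summarised under placebo.

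**Working it through.** The plan gives no figure on this point. Its sample-size statement (SD 9, difference 11, 12 per arm, two-sided 5%) reproduces, with power of 81.6% by the exact t-test, and nothing below changes it.

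**Set membership.** Inputs are the SAP 5.1 definitions: Full = enrolled and randomised; Safety = Full and at least one dose. For an enrolled subject:

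| Randomised | Dosed | In Full | In Safety | Meets the dosed-but-not-randomised condition |
|---|---|---|---|---|
| yes | yes | yes | yes | no |
| yes | no | yes | no | no |
| no | yes | no | no | **yes** |
| no | no | no | no | no |

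The only combination that meets the condition lies outside both sets. The SAP 7.9 row (Safety) and the SAP 7.4/Appendix A row (Full) therefore each have 0 admissible combinations. On the enrolled set there is 1.

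**Where such a subject would and would not appear.**

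- Absent, because the output uses the safety set: all adverse event, laboratory, vital sign, spirometry and S-STS tables (SAP 10); the exposure and accountability tables and the accountability and batch listings (SAP 7.9); the narrative columns for SAEs, discontinuations and events of special interest (SAP 10.6).
- Present, because the output uses the enrolled set: the listing of relevant deviations (SAP 7.4), the adverse event listing (SAP 10.1), the death listing (SAP 10.1.1), the death column of the narrative listing (SAP 10.6), and the laboratory listings (SAP 10.2.4). The laboratory listings cover only subjects with a Grade 3 or 4 result, a positive pregnancy test or selected liver-test elevations.

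**Mixed exposure under SAP 5.2.** Inputs are 150 mg twice daily for 28 days, so 2 × 28 = 56 doses, and 8 doses per wallet (4 days × 2). The splits below are illustrative assumptions for a subject randomised to placebo.

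| Placebo doses | Zavegepant doses | Zavegepant, mg | Share of doses | Column under SAP 5.2 |
|---|---|---|---|---|
| 0 | 56 | 8,400 | 100% | zavegepant |
| 1 | 55 | 8,250 | 98.2% | placebo |
| 8 (one wallet) | 48 | 7,200 | 85.7% | placebo |

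The rule works symmetrically for a subject randomised to zavegepant.

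**Size of one misplaced subject.** Take 12 per arm, with x placebo and y zavegepant subjects having the event in the table as planned. Move one subject with the event from placebo to zavegepant:

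- Placebo: x/12 − (x−1)/11 = (12−x)/132. The maximum is at x = 1: 1/12 to 0/11, or 8.3 points.
- Zavegepant: (y+1)/13 − y/12 = (12−y)/156. The maximum is at y = 0: 0/12 to 1/13, or 7.7 points.
- With x = y = 6: 6/132 = 4.5 points and 6/156 = 3.8 points.

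**The case against.** The strongest reply is that nothing is hidden. The relevant-deviation listing on the enrolled set would name a dosed but non-randomised subject, and the adverse event and death listings would carry that subject's events. Wrong-drug dosing is counted in SAP 7.9, and Appendix A has a deviation row for drug received that differs from the randomised assignment; randomised subjects can fall into both. This stands, and it rules out the stronger reading that the safety data would be lost from the report. It does not rescue a table row that can only print zero.

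A second reply is that the errors are unlikely. The IWRS assigns one subject-specific kit of 8 wallets for the whole treatment (Protocol 9.3.1), the same kit is used through Visit 8 (Protocol 9.4), and the first dose follows randomisation on site (Protocol 10.2.2). A wrong-kit error would then usually last throughout. The subject would have no dose of the randomised treatment and would be placed by the drug received. This also stands. A reader might infer that the SAP 5.2 rule generally puts zavegepant exposure under placebo; the documents support that only for the residual case of mixed exposure.

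Third, the safety set follows the protocol, since the Treated population has the same restriction. That is correct: the defect is the mismatch inside the SAP, not a departure from the protocol.

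Fourth, SAP 5.2 is a stated rule. Replacing it with one under which any zavegepant dose decides the column would place 55 placebo doses plus one zavegepant dose under zavegepant. That trade-off is debatable, so the point here is only that the two sections must agree.

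**Conclusion.** The point holds in limited form. Two planned counts are zero by construction, and a dosed but non-randomised subject would be missing from every safety summary table, from the accountability listing and from the SAE narrative columns, while still appearing in the enrolled-set listings. SAP 5.1 and 5.2 also give conflicting directions for mixed exposure.

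The effect is nil if no such error occurs, and the documents neither report one nor give a rate. At the planned 12 per arm, one moved subject with an adverse event shifts the rates by at most 8.3 points on placebo and 7.7 points on zavegepant. A shift of 8.3 points in both arms, which 1/12 might suggest, cannot occur because the denominators become 11 and 13. SAP section 2 says the study ended early for low enrolment, so the actual arms may be smaller and each subject would weigh more; the documents give no final numbers.

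The conclusion assumes that the Core SAP, which was not available, does not override these definitions. SAP section 2 gives it precedence only where this SAP is silent or refers to it directly, and this SAP states its own sets and grouping rule. SAP 10.6 also lets a separate narrative scope document prevail over its narrative criteria, so the SAE narrative gap could be closed there.

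**What to change.** 1. Tabulate the SAP 7.9 row and the matching Appendix A row on the enrolled set. This costs one population change in each of two table specifications.
2. Summarise the safety data of any dosed but non-randomised subject. Either add a separate row, or define Safety as all enrolled subjects with at least one dose.
3. If Safety is widened, make three further edits. Restrict mITT explicitly to randomised subjects, because SAP 5.1 builds it from safety subjects and would otherwise admit someone with no randomised arm. State how the Follow-up set, built the same way, is handled. Record the departure from the protocol's Treated population in SAP 13. The separate row avoids all three edits.
4. Reconcile SAP 5.1 and 5.2 for mixed exposure with one stated rule. At minimum, flag in the safety tables every subject with incorrect drug at least once, so that any zavegepant exposure shown under placebo is visible. This costs one sentence and one derivation flag.

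The sample size and power are unchanged. The mITT efficacy analysis is unchanged too, provided mITT stays confined to randomised subjects.

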5.2. Treatment Groups

The two treatment groups are zavegepant and placebo. The safety analysis set is assessed by as-treated treatment group, the full and mITT analysis sets are assessed by as-randomized treatment group, and the enrolled analysis set is assessed overall.

If a subject receives ≥ 1 dose of planned randomized treatment then that subject is considered to have as-treated treatment group equal to as-randomized treatment group, and will be analyzed according to randomized treatment.

5.3. Subgroups

No subgroup analyses are planned.

This document is confidential.

6. General Aspects for Statistical Analysis

All statistical analyses are performed using SAS statistical software (Version 9.4 or higher).

6.1. General Methods

Refer to the Core SAP for descriptive statistics, counting rules, rounding rules, dictionaries for coding AEs, medical history, and non-study medications.

- Unless otherwise specified, summaries will be presented for each treatment group and overall.
- Continuous variables will be summarized using the number of observations (n), mean, standard deviation (SD), median, minimum, and maximum. Categorical variables will be summarized using number of observations (n), frequency and percentages of subjects.
- Unless otherwise specified, listings will be sorted by randomization status (randomized, not randomized), which is not displayed, subject ID, and visit and/or assessment date (and time) if applicable.
- If multiple assessments are conducted at a given time point or visit, the non-missing value closest to the target date/time for the visit is used; in the case of a tie, the last value collected is used. All assessment results will be listed.

6.2. Key Definitions

- Baseline is the last non-missing observation prior to first administration of study drug unless otherwise specified.
- Change from baseline will be calculated as post-baseline value minus baseline value. If either the baseline or post-baseline value is missing, the change from baseline is set to "missing".
- The Study Day is the day relative to the date of first administration of study drug, where Day -1 is the day before administration of zavegepant and Day 1 is the day of first administration of study drug.
- Study day will be calculated as:
 - Study day = date of assessment – date of first administration of study drug +1 if the date of assessment is on or after the date of first study drug administration; Otherwise: Study day = date of assessment – date of first administration of study drug.
- Follow-up day will be calculated from the study drug last date as:
 - Measurement date – study drug last date, if measurement date \geq study drug last date + 1; otherwise: Measurement date – study drug last date – 1, if measurement date $<$ study drug last date + 1.

This document is confidential.

6.3. Missing Data

All analyses will be based on observed data unless otherwise specified. For the purposes of assessing treatment emergence for AEs or classifying medications into prior/concomitant, the algorithms described in Section 7.1.2.3 of the Core SAP will be used to impute partially and completely missing dates.

6.4. Visit Windows

All subjects are to adhere to the protocol-specified visit schedule in [Table 2](#). Visits will be analyzed as captured in the database, no visit windows will be assigned.

This document is confidential.

SAP text Version: SAP text version 2.0 24-May-2023

Filing requirements: TMF

Page 20 of 42

7. Disposition, Demographic, Other Baseline Characteristics and Medication

